### **3.3 Inclusion Criteria**

**3.3.1** Histopathological diagnosis of differentiated or undifferentiated locally recurrent or metastatic NPC (WHO Stage II-III);

**3.3.2** Patients with clinical stage IVB NPC [Appendix I, AJCC staging system for nasopharyngeal cancer, 8th edition] after failure of first-line platinum-based chemotherapy (monotherapy or combination therapy) and second-line single-agent or combination chemotherapy or targeted therapy. Treatment failure is defined as progression during or after chemotherapy after recurrence/metastasis; progression within 6 months after concurrent chemoradiotherapy is considered first-line treatment. All regimen changes due to drug intolerance are not considered treatment failure;

**3.3.3** No history of other malignant tumors, and having no other malignant tumors at the time of diagnosis;

**3.3.4** Male or female patients aged 18–70 years;

**3.3.5** ECOG performance status score of 0–2;

**3.3.6** Estimated survival  $\geq 3$  months;

**3.3.7** Non-lactating women and those of childbearing age must have a negative pregnancy test (serum or urine) within 14 days prior to enrollment, and be willing to take effective contraceptive measures during the study;

**3.3.8** At least one measurable lesion per RECIST ( $\geq 10$  mm in longest diameter by B-scan, MRI or spiral CT scan, and having not undergone radiotherapy);

**3.3.9** Laboratory tests must meet the following criteria:

- Blood routine: Neutrophil count (ANC)  $\geq 1.5 \times 10^9/L$ , platelet count (PLT)  $\geq 100 \times 10^9/L$ , and hemoglobin (HGB)  $\geq 90$  g/L;
- Liver function: Total bilirubin  $\leq 1.5$  times the upper limit of normal (ULN); blood aspartate aminotransferase (AST) and blood alanine aminotransferase (ALT)  $\leq 2.5 \times$  ULN (or  $\leq 5 \times$  ULN for subjects with liver metastases); and alkaline phosphatase  $\leq 5 \times$  ULN;

- Renal function: Serum creatinine (Cr)  $\leq 1.5 \times$  ULN; and creatinine clearance  $\geq 50$  mL/min;
- Urinalysis: Urine protein  $< 2+$  (subjects with baseline urine protein of  $\geq 2+$  should undergo a 24-hour urine protein test within 7 days and can be enrolled only when urine protein  $< 1$  g);
- Coagulation function: INR and APTT  $\leq 1.5 \times$  ULN;

**3.3.10** No severe cardiopulmonary dysfunction;

**3.3.11** Sign the informed consent form;

**3.3.12** Ability to comply with the study protocol.

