## **6.3 Methods of Efficacy Evaluation**

Efficacy is primarily evaluated by MRI, CT, or nasopharyngoscopy at the site of lesion. Refer to RECIST 1.1 for specific evaluation criteria.

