## **15. APPENDIX**

### **Appendix I Staging of Nasopharyngeal Carcinoma (AJCC/UICC 8th Edition)**

Primary tumor (T)

Tx Primary tumor cannot be assessed

Tis Carcinoma in situ

T0 No tumor identified, but EBV-positive cervical node(s) involvement

T1 Tumor confined to nasopharynx, or extension to oropharynx and/or nasal cavity without parapharyngeal involvement\*

T2 Tumor with extension to parapharyngeal space and/or adjacent soft tissue involvement (medial pterygoid, lateral pterygoid, prevertebral muscles)

T3 Tumor with infiltration of bony structures at skull base, cervical vertebra, pterygoid structures, and/or paranasal sinuses

T4 Tumor with intracranial extension, involvement of cranial nerves, hypopharynx, orbit, parotid gland, and/or extensive soft tissue infiltration beyond lateral surface of the lateral pterygoid muscle

Regional lymph nodes (N)

Nx Regional lymph nodes cannot be assessed

N0 No regional lymph node metastasis

N1 Unilateral cervical, unilateral or bilateral retropharyngeal lymph nodes, above the caudal border of cricoid cartilage;  $\leq 6$  cm

N2 Bilateral metastasis in lymph node(s), 6 cm or less in greatest dimension, above the caudal border of cricoid cartilage

N3 > 6 cm and/or below caudal border of cricoid cartilage (regardless of laterality)

Distant metastasis (M)

M0 No distant metastasis

M1 Distant metastasis

Stage 0 Tis N0 M0

Stage I T1 N0 M0

Stage II T0–1 N1 M0, T2 N0–1M0

Stage III T0–2 N2 M0, T3 N0–2 M0

Stage IVA T0–3 N3 M0 or T4 N0–3 M0

Stage IVB Any T, N and M1

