1.1.1 Measurable lesions

Tumor lesions: Must be accurately measured in at least one dimension (the longest diameter in the plane of measurement is to be recorded) with a minimum size of:

- 1) 10 mm for CT scan (CT slice thickness is not more than 5 mm)
- 2) 10 mm for routine clinical instruments (tumor lesions that cannot be accurately measured with calipers should be recorded as unmeasurable)

- 3) 20 mm for chest X-ray
- 4) Malignant lymph nodes: Lymph nodes are pathologically enlarged and measurable, and the short axis of an individual lymph node in CT scan must be  $\geq$  15 mm (the recommended CT slice thickness is not more than 5 mm). At baseline and during follow-up, only the short axis will be measured and followed.

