### Evaluation method

The same method of assessment and the same technique should be used to characterize each identified and reported lesion at baseline and during follow-up. Imaging-based evaluation should always be done rather than clinical examination unless the lesion(s) being followed cannot be imaged but are assessable by clinical exam.

Clinical lesions: Clinical lesions will only be considered measurable when they are superficial and 10 mm in diameter as assessed using calipers (e.g. skin nodules). For the case of skin lesions, documentation by color photography including a ruler to estimate the size of the lesion is suggested. As noted above, when lesions can be evaluated by both clinical exam and imaging, imaging evaluation should be undertaken since it is more objective and may also be reviewed at the end of the

study.

**Chest X-ray:** Chest CT is preferred over chest X-ray, particularly when progression is an important endpoint, since CT is more sensitive than X-ray, particularly in identifying new lesions. However, lesions on chest X-ray may be considered measurable if they are clearly defined and surrounded by aerated lungs.

**CT, MRI:** CT is the best currently available and reproducible method to measure lesions selected for response assessment. This guideline has defined the measurability of lesions on CT scans based on the assumption that CT slice thickness is 5 mm or less. If the CT slice thickness is greater than 5 mm, the minimum size of a measurable lesion should be twice the slice thickness. MRI is also acceptable in certain situations (e.g., for body scans).

**Ultrasound:** Ultrasound is not useful in the assessment of lesion size and should not be used as a method of measurement. Ultrasound examinations cannot be reproduced in their entirety for an independent review at a later date and, because they are operator-dependent, it cannot be guaranteed that the same technique and measurements will be taken from one assessment to the next. If new lesions are identified by ultrasound in the course of the trial, confirmation by CT or MRI is advised. If there is concern about radiation exposure at CT, MRI may be used instead of CT in selected instances.

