**Endoscopy, laparoscopy:** The utilization of these techniques for objective tumor evaluation is not advised. However, they can be useful to confirm complete pathological response when biopsies are obtained or to determine relapse in trials where recurrence following complete response or surgical resection is an endpoint.

**Tumor markers:** Tumor markers alone cannot be used to assess objective tumor response. If markers are initially above the upper normal limit, however, they must normalize for a patient to be considered in complete response. Because tumor markers are disease-specific, instructions for their measurement should be incorporated into protocols on a disease-specific basis. Specific guidelines for both CA-125 response (in recurrent ovarian cancer) and PSA response (in recurrent prostate cancer) have been published. In addition, the Gynecologic Cancer Intergroup has developed

CA-125 progression criteria which are to be integrated with objective tumor assessment for use in first-line trials in ovarian cancer.

Cytology/histology: These techniques can be used to differentiate between PR and CR in rare cases if required by protocol (for example, residual lesions in tumor types such as germ cell tumors, where known residual benign tumors can remain). When effusions are known to be a potential adverse effect of treatment (e.g., with certain taxane compounds or angiogenesis inhibitors), the cytological confirmation of the neoplastic origin of any effusion that appears or worsens during treatment can be considered if the measurable tumor has met criteria for response or stable disease in order to differentiate between response (or stable disease) and progressive disease.

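### Inclusion criterion 3.3.8 admits lesions that Appendix II calls non-measurable, and 3.3.2 (stage IVB, hence M1) shuts out the M0 recurrences that 3.3.1, 3.1 and the title include

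*Protocol*

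**What the plan says.** **Measurable disease.** Protocol 3.3.8 requires at least one lesion measurable by RECIST and explains this in parentheses as at least 10 "mm in longest diameter by B-scan, MRI or spiral CT scan", not previously irradiated. It has no separate rule for lymph nodes. Section 6.1 makes RECIST 1.1, reproduced in Appendix II, the standard for efficacy. Appendix II states: "Ultrasound is not useful in the assessment of lesion size and should not be used as a method of measurement". For nodes, its section 1.1.1 says the "short axis of an individual lymph node in CT scan must be" at least 15 mm, and 1.1.2 places nodes with a short axis of 10 to under 15 mm among the non-measurable lesions.

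**Stage.** 3.3.1 admits "differentiated or undifferentiated locally recurrent or metastatic NPC". 3.3.2 is limited to "Patients with clinical stage IVB NPC" as staged in Appendix I, where the entry reads "Stage IVB Any T, N and M1". The title, the primary objective (2.1) and the target population (3.1) all speak of recurrent or metastatic disease.

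**Related wording.** 3.5.2 lists B-scan among the imaging that can document progression for withdrawal. Section 6.3 says: "Efficacy is primarily evaluated by MRI, CT, or nasopharyngoscopy at the site of lesion". On endoscopy, Appendix II says: "The utilization of these techniques for objective tumor evaluation is not advised".

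**The concern.** The primary endpoint is DCR by RECIST 1.1, and 6.2.2 counts CR, PR or SD as best response. In Appendix II (2.1), PR and SD for target disease rest on the sum of target-lesion diameters. If entry is decided by a looser test than the one that defines a target lesion, some patients can enter without the baseline measurement the endpoint uses. Two sites could also decide the same patient differently, one by the words referring to RECIST and the other by the parenthesis.

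The stage criterion bears on what the trial can conclude. Applied as written, it yields a metastatic (M1) sample, while the title and objective promise a result for recurrent or metastatic disease.

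**Working it through.** No figure in the protocol depends on these clauses, so the check is mainly a comparison of texts.

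**1. 3.3.8 against Appendix II**

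| Feature | 3.3.8 parenthesis | Appendix II |
|---|---|---|
| Ultrasound | accepted | not to be used for measuring (1.2) |
| Node | at least 10 mm, longest diameter | at least 15 mm, short axis (1.1.1) |
| Node with 10 to <15 mm short axis | accepted | non-measurable (1.1.2) |
| CT slices above 5 mm | no condition | minimum size is twice the slice thickness (1.2) |
| Irradiated lesion | barred outright | usually not measurable unless progression in it is shown (1.1.3) |

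Example: a node 12 mm long with an 8 mm short axis passes the parenthesis, yet Appendix II (2.2) treats a short axis below 10 mm as normal. The first four rows show 3.3.8 looser than Appendix II. The last shows it stricter.

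**2. Consequence for DCR.** Without a target lesion there is no target sum, so PR and SD cannot be assigned on one. PD remains available: Appendix II 2.4 covers patients with only non-measurable disease, and 2.5 makes an unequivocal new lesion progression. The Appendix II response table with columns for non-target lesions, new lesions and overall response (printed under the Table 1 caption) gives CR, non-CR/non-PD, not evaluated or PD. A note after the tables prefers non-CR/non-PD to SD for non-target disease. Section 6.2.2 does not say whether that category counts as disease control.

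**3. How far mandatory imaging helps.** Sections 5.1 and 5.3 require CT or MRI of nasopharynx, neck, chest and abdomen with pelvis at screening and every 6 weeks, under baseline conditions. A lesion first seen on B-scan in those regions would therefore also have a CT or MRI baseline. This does not change the size a node must reach, so the nodal conflict remains.

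**4. 3.3.2 against the stated population.** In Appendix I the highest M0 stage is IVA, so no M0 patient is IVB. An M0 local recurrence passes 3.3.1 and fails 3.3.2. A patient with local recurrence and distant metastases passes both.

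**5. Scale, under an assumption.** The protocol gives no share f of patients without a target lesion. Suppose they are all counted as not controlled and the others have the design's 40% DCR. With the rule in 3.2 (at least 11 of 35), power = P(X ≥ 11), where X is binomial with n = 35 and p = 0.40 × (1 − f):

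| f | p | Power |
|---|---|---|
| 0 | 0.40 | 0.888 |
| 5% | 0.38 | 0.835 |
| 10% | 0.36 | 0.768 |
| 20% | 0.32 | 0.592 |

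If instead non-CR/non-PD counted as control, and these patients were controlled as often as the rest, power would stay at 0.888. The table shows how much could hang on the unstated convention. It does not estimate f.

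**The case against.** The best defence is that 3.3.8 opens by requiring measurability by RECIST, so a careful site would apply Appendix II. CT or MRI is compulsory, and ultrasound is absent from the response methods in 6.3. This largely answers the ultrasound concern. It does not answer the nodal one, because the parenthesis is the test a site will apply and it sets a different threshold on a different axis.

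On stage, inclusion criteria are cumulative, so 3.3.2 can simply narrow 3.3.1. The trial can run that way, but its title, objective and target population would then be broader than its sample.

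The defence also stands in part on 6.3: it defers to RECIST 1.1 for the criteria, and Appendix II allows endoscopy to confirm complete pathological response or determine relapse. Likewise, Appendix II foresees ultrasound detecting new lesions, with CT or MRI confirmation advised, so naming B-scan in 3.5.2 is not wholly at odds with it.

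A reader might infer four stronger points that the protocol does not support:

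- **That 3.3.2 contradicts Appendix I.** It uses Appendix I consistently. The conflict is with 3.3.1, 3.1, the objective and the title.
- **That a patient without measurable disease cannot be classed as PD.** Appendix II provides for it.
- **That ineligible patients can be dropped once their outcome is known.** The full analysis set in 9.2 excludes significant eligibility violators but does not say when this is decided, and stage is a baseline fact.
- **That each affected patient moves DCR by 1/35 = 2.9 points, so one could decide the trial.** That holds only for reclassification among 35; among 39 it is 1/39 = 2.6. Exclusion also lowers the denominator: from 11/35 = 31.4%, removing an uncontrolled patient gives 11/34 = 32.4%, and removing a controlled one gives 10/34 = 29.4%. One patient matters only at the cut-off, as in any such trial.

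**Conclusion.** Both conflicts stand. As written, the parenthesis in 3.3.8 admits patients with no measurable lesion under Appendix II, chiefly those with small nodes only. Read with Appendix I, 3.3.2 excludes M0 recurrences that the rest of the protocol says it studies. The first affects whether DCR can be assigned as defined; the second affects the population to which the result applies. Neither can be sized from the protocol, since it gives no share of node-only or M0 patients, and the power figures above rest on an assumed share and an assumed convention. The wording in 3.5.2 and 6.3 is a lesser inconsistency. The entry criteria should be corrected, but nothing here shows that the trial's result would be wrong.

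**What to change.** 1. **3.3.8.** Replace the parenthesis with: measurable per Appendix II (non-nodal at least 10 mm longest diameter, nodal at least 15 mm short axis), not by ultrasound. Referring to Appendix II also brings in its slice-thickness rule and keeps its provision for superficial lesions measured with calipers.
2. **Irradiated lesions.** Reconcile the outright bar in 3.3.8 with Appendix II 1.1.3, which allows such lesions after shown progression and asks protocols to state the conditions. Otherwise, even if 3.3.2 is widened, a recurrence lying only in an irradiated field would still fail 3.3.8.
3. **3.3.2.** Either let it cover recurrent disease as well as stage IVB, or keep it and restate the title, objective, target population and conclusion as metastatic (M1) disease. The choice is the sponsor's.
4. **DCR.** State whether non-CR/non-PD counts as disease control for any patient enrolled without a target lesion.
5. **3.5.2 and 6.3.** Reconcile the mention of B-scan and of nasopharyngoscopy with Appendix II. No particular withdrawal rule is proposed here.

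The cost is wording only, since CT or MRI is already required at baseline and every 6 weeks. Some node-only candidates may become ineligible; how many cannot be told from the protocol.

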### **6.2.2 Definition of endpoints**

Disease control rate (DCR) is defined as the percent of subjects with complete response (CR), partial response (PR) or stable disease (SD) as the best overall response;

Overall response rate (ORR) is defined as the percent of subjects with CR or PR as the BOR;

Progression free survival (PFS) is defined as the time from enrollment to PD or death due to any cause. For subjects with unknown disease status, PFS refers to the time from enrollment to last the follow-up;

Overall survival (OS) is defined as the time from enrollment to death due to any cause. If it is unclear whether the subject has died, OS refers to the time from enrollment to the last follow-up;

Complete remission (CR) is defined as the percent of subjects with CR as BOR.

Partial remission (PR) is defined as the percent of subjects with PR as BOR.

Duration of response (DOR) is defined as the time from the first documented response (CR or PR) to progressive disease (PD) or recurrence.

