#### 1.1.2 Non-measurable lesions

All other lesions, including small lesions (the longest axis  $<$  10 mm or pathological lymph nodes with short axis  $\geq$  10 mm to  $<$  15 mm) , and non-measurable lesions. Lesions considered truly non-measurable include: leptomeningeal disease, ascites, pleural or pericardial effusion, inflammatory breast cancer, lymphangitic involvement of skin or lung and abdominal masses identified by a physical exam that is not measurable by reproducible imaging techniques, and cystic lesions.

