## 2. Tumor response evaluation

### 2.1 Evaluation of target lesions

Complete response (CR): Disappearance of all target lesions. Any pathological lymph nodes (whether target or non-target) must have a reduction in the short axis to < 10 mm.

Partial response (PR): At least a 30% decrease in the sum of diameters of target lesions, taking as reference the baseline sum diameters.

Progressive disease (PD): At least a 20% increase in the sum of diameters of target lesions, taking as reference the smallest sum in the study (this includes the baseline sum if that is the smallest in the study). In addition to the relative increase of 20%, the sum must also demonstrate an absolute increase of at least 5 mm. (Note: The appearance of one or more new lesions is also considered progression).

Stable disease (SD): Neither sufficient shrinkage to qualify for PR nor sufficient increase to qualify for PD, taking as reference the smallest sum diameters while on the study.

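### The bracket in inclusion criterion 3.3.8 defines a measurable lesion differently from Appendix II (node size, ultrasound, CT slice thickness), so a patient without a RECIST target lesion could enter the DCR analysis

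*Protocol*

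**What the plan says.** Protocol 3.3.8 opens with "At least one measurable lesion per RECIST". Its bracket then sets a threshold of 10 "mm in longest diameter by B-scan, MRI or spiral CT scan, and having not undergone radiotherapy". That is one size, one axis and three imaging methods. Lymph nodes are not mentioned.

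Appendix II is more detailed:

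- Section 1.1.1, non-nodal lesions: "10 mm for CT scan (CT slice thickness is not more than 5 mm").
- Section 1.1.1, nodes: "the short axis of an individual lymph node in CT scan must be" at least 15 mm, and only the short axis is measured and followed.
- Section 1.1.2: the non-measurable group includes "pathological lymph nodes with short axis" from 10 mm to below 15 mm.
- Section 1.2: "Ultrasound is not useful in the assessment of lesion size and should not be used as a method of measurement". For CT slices thicker than 5 mm, the smallest measurable size is twice the slice thickness.

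The primary endpoint is DCR. Section 6.2.2 counts patients with CR, "partial response (PR) or stable disease (SD) as the best overall response". Section 3.2 calls the drug effective if at least 11 patients are controlled, with 35 patients required and 39 planned.

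**The concern.** DCR depends on RECIST categories, and those depend on whether the patient has a target lesion. If the entry criterion and the response criteria define measurability differently, a patient can be properly enrolled under one text and have no target lesion under the other. Appendix II then scores that patient on a scale without PR or SD, the two categories that usually supply most of a DCR count. Someone has to decide after the event whether such a patient is controlled. With a cut-off of 11, one or two decisions of that kind could settle the result.

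Nodes matter in this disease. Staging in Appendix I has an N category, and 3.3.2 requires stage IVB, which means distant metastasis. Unirradiated distant nodes are therefore possible, and the no-radiotherapy condition does not remove the problem.

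**Working it through.** **Step 1. The two texts side by side.**

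| Item | 3.3.8 bracket | Appendix II | Agree? |
|---|---|---|---|
| Non-nodal lesion on CT | ≥10 mm longest diameter | ≥10 mm longest diameter, slice ≤5 mm | Yes, for thin slices |
| Thicker CT slices | No condition | Minimum = 2 × slice thickness, so more than 10 mm once the slice exceeds 5 mm | No |
| Lymph node | No separate rule | ≥15 mm short axis; 10 to <15 mm is non-measurable | No |
| Ultrasound (B-scan) | Allowed | Not to be used for measurement | No |

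**Step 2. A patient on whom the texts disagree.** Take a single unirradiated node, long axis 16 mm, short axis 12 mm. Under the bracket, 16 ≥ 10, so the patient qualifies. Under Appendix II, 12 < 15, so the node is not measurable; since 10 ≤ 12 < 15, it is a non-measurable lesion. The patient has non-target disease only. The same holds for a lesion that can be measured only by B-scan.

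**Step 3. Analysis set.** Section 9.2 removes significant eligibility violators from the FAS. By the bracket this patient has violated nothing and stays in. By the general reference to RECIST the patient is ineligible and may be removed. The same patient is thus in or out of the primary analysis according to which half of 3.3.8 is read.

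**Step 4. Scoring.** For non-target disease, Appendix II 2.3 and the response grid in 2.7 give CR, non-CR/non-PD or PD (or not evaluated). The note in 2.7 prefers non-CR/non-PD to SD for such disease. Section 6.2.2 does not say whether that category counts towards DCR.

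**Step 5. What this could do to the count (illustration only).** Inputs from section 3.2: null DCR 20%, alternative 40%, type I error 5%, power 80%, dropout 10%.

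The plan's sample size reproduces. With an exact one-sided binomial test, the smallest n meeting both targets is 35 with success at 12 or more (type I error 0.0344, power 0.8048), and 35/0.9 = 38.9, rounded up to 39. The printed cut-off of 11 in 35 gives type I error 0.0747 and power 0.8877. That is a separate matter and serves here only as the starting point.

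Let k of the 35 have no target lesion. The documents give no value for k; 1 to 3 is an assumption to show the scale.

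- Never counted as controlled: power = P(Bin(35−k, 0.4) ≥ 11), type I error = P(Bin(35−k, 0.2) ≥ 11).
- Always counted as controlled (an extreme bound): type I error = P(Bin(35−k, 0.2) ≥ 11−k), power = P(Bin(35−k, 0.4) ≥ 11−k).

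| k | Never: power | Never: type I error | Always: power | Always: type I error |
|---|---|---|---|---|
| 0 | 0.888 | 0.075 | 0.888 | 0.075 |
| 1 | 0.862 | 0.062 | 0.927 | 0.125 |
| 2 | 0.831 | 0.051 | 0.956 | 0.200 |
| 3 | 0.795 | 0.041 | 0.975 | 0.302 |

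The two treatments move the operating characteristics in opposite directions, and the documents do not choose between them.

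**The case against.** The strongest reply is that the operative words of 3.3.8 are the reference to RECIST. RECIST 1.1 is the stated standard in sections 2.3 and 6.1 and is reproduced in Appendix II. On that reading the bracket abbreviates the non-nodal rule, and a node below 15 mm short axis is simply ineligible. This reply stands in part. The criterion never says that small nodes qualify, and a reader who infers that it does is relying on its silence. But the bracket cannot be only shorthand for Appendix II, because it allows a method that Appendix II rules out. The criterion has two readings that give opposite decisions for the same patient.

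The affected group is also narrow. A patient needs distant metastasis yet no unirradiated lesion that Appendix II accepts as measurable. Sections 5.1 and 5.3 specify CT or MRI at screening and every six weeks, which limits the practical reach of the B-scan wording. Both points stand and keep the expected number low.

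Two stronger readings are tempting, and the documents support neither:

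- **A normal-sized node could enter and count as CR at baseline.** For CR, Appendix II 2.1 says pathological nodes "must have a reduction in the short axis to" below 10 mm, so a node already below that might seem to qualify from the start. But section 2.2 defines a node below 10 mm short axis as normal. It is not a lesion, so it does not satisfy 3.3.8 on any reasonable reading.
- **Patients without a target lesion are controlled whatever the drug does, so type I error is inflated.** Sections 2.3 to 2.5 of Appendix II still score PD for unequivocal non-target progression or any new lesion, a real route in stage IVB disease after two failed lines.

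**Conclusion.** The point holds as a conflict between an entry criterion and the trial's own response criteria. The bracket in 3.3.8 departs from Appendix II on nodes, on ultrasound and on slice thickness. Read literally, it lets in a patient with no Appendix II target lesion, whose likely category while the lesion persists is not named in the DCR definition.

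The consequence is an undefined count for a few patients, not a bias of known size or sign. The tabulated changes rest on an assumed k and on all-or-nothing counting; they show that a few patients could matter at a cut-off of 11 and are not an estimate of what will happen. Neither the sample size nor the analysis method is called into question by this point. It should be corrected because the correction is simple and protects the primary endpoint.

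**What to change.** Replace the size and method bracket in 3.3.8 with a reference to Appendix II 1.1.1: a non-nodal lesion of at least 10 mm in longest diameter, or a lymph node of at least 15 mm in short axis, by CT with slices of at most 5 mm or by MRI. Keep the condition that the lesion has not been irradiated. Delete B-scan from this line.

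The cost is a one-line amendment. A few patients with only small nodal disease become ineligible, as Appendix II already implies. The planned 35 and 39 patients do not change.
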